9.3.17.2 Actual Treatment and Dose Level for a Medication Record

Since a medication could be a prior medication and be taken during Treatment Periods, flag variables will be used to identify a medication record that was taken while a subject received placebo, tildacerfont 50 mg, tildacerfont 100 mg, and/or tildacerfont 200 mg.

A medication record will be assigned to the first study treatment and dose level when the subject was on and was taking the medication during the Treatment Period. For example, if a subject starts a new medication while taking tildacerfont 100 mg then later dose escalated to 200 mg QD at Week 8, the treatment and dose level will be tildacerfont 100 mg for that medication record.

9.4 Analysis Windows

Analysis visits will match the protocol-specified visits (Screening, Day 1, Week 4, Week 8, Week 12, and Follow-up). Unscheduled clinical visits may be used to capture missed or partially completed clinical visits; therefore, analysis visits and their windows are defined using Study Day (See [Section 9.3.2](#)). For the purposes of data analysis and summary, assessments and/or measurements the protocol-specified visit will be preferentially flagged for analysis. In the absence of a protocol-specified visit, the analysis flag will be based on the collection date/time that is closest to the protocol-scheduled time point (or target Study Day). Analysis visit windows are presented in [Table 4](#).

Table 4 Analysis Visit Windows (Clinic Visits Only)

Protocol Specified Visit Number	eCRF Visit Label	Analysis Visit	Target Study Day	Start (days)	Stop (days)
	Screening	Screening	-15	low	-7
Visit 1	Treatment P1 V1	Day 1	1	-6	14
Visit 2	Treatment P1 V2	Week 4	29	15	43
Visit 3	Treatment P2 V3	Week 8	57	44	71
Visit 4	Treatment P3 V4	Week 12	85	72	100
Visit 15	Follow up	Follow-up	Last dose	Last dose +1	Last dose +30

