1.2. Study Rationale

1.2.1. Rationale for the Study Design

The SPR001-210 study is a randomized, placebo-controlled, dose escalation study that will evaluate the preliminary efficacy and safety of tildacerfont (50 mg, 100 mg, and 200 mg once daily [QD]) compared to placebo after 12 weeks of double-blind treatment in subjects with PCOS and elevated adrenal androgens at baseline. Subjects randomized to the tildacerfont group will receive 3 escalating dose levels of tildacerfont with each dose level administered for 4 weeks. All subjects randomized to placebo will remain on placebo over the full 12-week treatment period. To be able to characterize changes and the magnitude of changes in DHEAS as due to treatment and to account for any inherent variability in DHEAS, a placebo treatment group is warranted. Four weeks of treatment was deemed minimally adequate to observe change in hormones and androgens, given the exposure profile of tildacerfont which achieves steady state after approximately 2 weeks of dosing.

DHEAS is the primary hormone being evaluated in this study and was selected as a stable biomarker of androgen production. Additionally, reduction in DHEAS was chosen as the efficacy endpoint as the vast majority (>90%) of DHEAS is produced in the adrenal glands and is therefore representative of an adrenal source of hyperandrogenemia, which is the population that may potentially be addressed with tildacerfont. The level of receptor occupancy necessary to result in reduction in DHEAS in subjects with PCOS is unknown. A dose of 50 mg is expected to result in ≤50% receptor occupancy while a dose of 200 mg is expected to provide ≥90% receptor occupancy. The range of doses was chosen to understand if increasing dose can provide additional reductions in DHEAS levels.

Additionally, the study will provide preliminary safety data over up to 12 weeks of treatment with tildacerfont in the PCOS population. Safety visits are planned every 4 weeks at the end of each treatment period at a dose level with a scheduled telephone call 2 weeks after initiating each tildacerfont dose level. The level of safety monitoring should provide adequate oversight

given the observed safety and tolerability profile to date. The study population will include women (18 to 40 years of age) with PCOS, characterized by the presence of hyperandrogenemia as indicated by a screening serum DHEAS level > age-matched reference ULN.

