1.2.2. Rationale for Study Drug Dosing

Tildacerfont tablets will be administered starting at 50 mg and up to 200 mg QD. The long half-life of tildacerfont, approximately 60 hours after single-dose administration, supports QD dosing in this study.

The safety data from previous Phase 1 and Phase 2 studies show that tildacerfont at a dose of \leq 200 mg/day has been generally well tolerated. The most common non-procedural adverse events (AEs) reported in completed studies, across all dose levels, were headache, diarrhea, constipation, nausea, and cough. No serious adverse events (SAEs) related to study drug have been observed to date.

In studies with CAH patients (n=26) with 2 to up to 12 weeks of treatment at total daily doses of \geq 200 mg, the most common AEs were upper respiratory tract infection (n=4) and contusion, diarrhea, and headache (all n=3).

Healthy adult subjects have been dosed with similar amounts of tildacerfont (50 mg [n=8], 150 mg [n=9], and 200 mg QD [n=6]) for up to 14 days in a Phase 1 study. Tildacerfont did not produce a clinically significant change in ACTH levels in healthy subjects with normal baseline ACTH levels, nor change the 24-hour diurnal cortisol concentration profile, the cortisol area under the plasma concentration vs time curve from time zero to 5 hours post-dose (AUC_{0-5hr}) or affect the cortisol surge response to a hypoglycemic stressor (post an insulin tolerance test).

Post insulin tolerance test cortisol profiles for tildacerfont treated subjects were indistinguishable from placebo with tildacerfont/placebo AUC_{0-5hr} ratios from 1.13 to 1.19.

Additionally, no AEs of adrenal insufficiency have been noted in the completed studies to date.

The starting dose of 50 mg was based on the minimum level of CRF₁ receptor engagement reasonably expected to have an effect in patients with PCOS.

Given the observed safety profile to date, doses from 50 to 200 mg were deemed appropriate in this PCOS Investigational New Drug (IND) opening study.

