9.3.17 Subject-Level Study Treatment

This study consists of Screening, Treatment, and Follow-up periods. For a data record, the planned treatment and dose level will be based on a specific study period as follows:

Study Period	Planned Treatment
Screening	Placebo or tildacerfont (50 mg QD)
Treatment Period (Day 1 to Week 4)	Placebo or tildacerfont (50 mg QD)
Treatment Period (post-Week 4 to Week 8)	Placebo or tildacerfont (100 mg QD)
Treatment Period (post-Week 8 to Week 12)	Placebo or tildacerfont (200 mg QD)

The actual study drug treatment and dose level will be the study drug and dose level a subject was on when a data record was measured/assessed.

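### SAP Table 4 lets a DHEAS redraw taken after dose escalation be analysed as the earlier dose at Week 4 or Week 8

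*SAP*

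**What the plan says.** SAP 9.4 gives first place to the record from the protocol-specified visit. It also foresees gaps: "Unscheduled clinical visits may be used to capture missed or partially completed clinical visits". When the scheduled record is absent, "the analysis flag will be based on the collection date/time that is closest to the protocol-scheduled time point". The rows of Table 4 (target day, start, stop) are "Treatment P1 V2 Week 4 29 15 43", "Treatment P2 V3 Week 8 57 44 71" and "Treatment P3 V4 Week 12 85 72 100". The rule sets no condition on dose or on time since the last dose.

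SAP 10.3.1 adds a second route. A retest replaces a first test that was invalidated, with haemolysis as the example, and no date limit is given.

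On timing, SAP 5.1 moves tildacerfont subjects to 100 mg at Week 4 and to 200 mg at Week 8. SAP 9.3.14.3 presumes that each new level starts on the dispensing date at those visits. The protocol synopsis puts the clinic visits on Days 28, 56 and 84. The schedule footnotes (Protocol 12.2) allow ±1 day and place the blood draws at about 8 A.M. Protocol 5.1 has the drug taken between 6 P.M. and midnight.

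On analysis, SAP 13 compares each dose with placebo. The ANCOVA (SAP 13.1.3.1) contains randomized group, log baseline DHEAS and age. The MMRM (SAP 13.1.3.2) adds time and its interaction with group. Neither has a dose term. SAP 9.3.17 does define an actual dose for each record, namely "the study drug and dose level a subject was on when a data record was measured/assessed", but the DHEAS models do not use it.

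**The concern.** Midpoint windows suit a trial in which treatment is constant between visits. Here treatment changes at the visit, so the second half of each window belongs to the next dose. Suppose a subject attends on Day 28, takes home the next supply and starts 100 mg that evening, and the laboratory then reports the DHEAS sample as unusable. A redraw a week or two later is inside the Week 4 window and is analysed as a 50 mg result.

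The study asks whether increasing dose lowers DHEAS further (Protocol 1.2.1), and the Week 4 and Week 8 comparisons carry that question. If DHEAS does fall with dose, such records make the lower dose look better than it is and flatten the apparent dose response. At Week 12 a late redraw from someone who has finished dosing would act the other way, because it is off drug.

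**Working it through.** **1. Reproduce the windows.** The Table 4 targets are Days 1, 29, 57 and 85. Their midpoints are (1+29)/2 = 15, (29+57)/2 = 43 and (57+85)/2 = 71. The last two are the Week 4 and Week 8 stop days. The Week 12 stop is 85 + 15 = 100. The windows therefore follow from visit spacing, not from dosing.

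**2. Count the days after the dose change.** With a morning draw and an evening dose on the visit day, every later day follows the change.

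| Window | Days | Length | Nominal visit | Days after visit | Share |
|---|---|---|---|---|---|
| Week 4 | 15-43 | 43-15+1 = 29 | 28 | 43-28 = 15 | 52% |
| Week 8 | 44-71 | 71-44+1 = 28 | 56 | 71-56 = 15 | 54% |
| Week 12 | 72-100 | 100-72+1 = 29 | 84 | 100-84 = 16 | 55% |

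If the visit is one day late, within the protocol's tolerance, the counts are 14, 14 and 15.

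**3. How far into the next dose.** Protocol 1.2.2 gives a half-life of "approximately 60 hours after single-dose administration", and Protocol 1.2.1 says that the drug "achieves steady state after approximately 2 weeks of dosing". The approach to the new steady state is 1 - 2^(-t/60 h).

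- 3 days after the change: 57%
- 7 days: 86%
- Day 43: from the evening of Day 28 to that morning is 14.5 days = 348 h = 5.8 half-lives, or 98%
- Day 71: the same interval from the evening of Day 56, so also 98%, now into 200 mg

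**4. Target day.** Targets 29, 57 and 85 are each one day after the protocol visit day. For a subject seen on Day 28, the Week 4 target morning already follows the first 100 mg dose. Between two unscheduled samples, one on Day 30 (1 day from target, on 100 mg) would be chosen over one on Day 27 (2 days from target, on 50 mg).

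**5. Week 12.** Assume the last dose is taken on the evening of Day 84. A sample on the morning of Day 100 is then 15.5 days = 372 h = 6.2 half-lives later, with about 99% of the drug washed out.

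**6. Weight of one record.** Placebo subjects do not change dose, so only tildacerfont records can be misassigned. With the planned 26 subjects, one record carries 1/26 = 3.8% of the arm mean, and one responder moves the arm's proportion by 3.8 percentage points. SAP 15 says that the study stopped early with a small sample, so the actual weight is larger. The actual number is not given.

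**7. Search for a safeguard.** SAP 14.2 summarises safety laboratories by actual treatment received, which handles those tables. No comparable condition applies to the DHEAS ANCOVA, the MMRM or the responder models.

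**The case against.** The trigger is narrow, and this stands. The scheduled visit is always preferred, and only telephone contacts lie between clinic visits. The unscheduled returns that the protocol describes are for cortisol or liver tests, not DHEAS. Escalation is tied to dispensing, so a wholly late visit also delays the new dose and its sample is not on the higher level. The problem needs a visit that took place with drug dispensed, an unusable or missing DHEAS sample, and a redraw before the next visit.

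The magnitude is also a worst case. Days 43 and 71 are window edges, while the rule takes the sample nearest the target. The 60 h figure is a single-dose half-life, and steady state refers to drug level, not DHEAS. Protocol 1.2.1 regards four weeks as only just enough to see hormone change, so two weeks on 100 mg need not show the full DHEAS response. This limits the size of the error but does not make the dose label right.

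Three stronger readings are tempting, and the documents do not support them:

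- A reader might infer that SAP 9.3.17 and 9.4 contradict each other. They define different attributes, the dose of a record and its analysis visit, and one record can carry both. The gap is that the efficacy models use only the visit.
- A reader might infer that every off-drug Week 12 value is misplaced. The primary estimand (SAP 13.1.1) is treatment policy and sets discontinuation aside, so Week 12 values from subjects who stopped early belong in the analysis. The secondary analysis already counts discontinuation as non-response.
- A reader might infer from the Day 1 window, which runs to Day 14, that a post-dose value could become baseline. SAP 9.3.7 requires a value before the first dose.

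**Conclusion.** The point holds in a limited form. As written, SAP 9.4 and 10.3.1 allow a DHEAS sample taken on the next dose level to be analysed as Week 4 or Week 8. About half of each window lies after escalation, and no efficacy rule corrects the assignment. At Week 12 the issue is confined to late fallback or retest samples from subjects who completed dosing.

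The number of affected records cannot be computed from the documents and is probably small. The day counts assume on-schedule visits, morning draws and a new level started on the evening of the visit. The percentages assume the 60 h half-life and describe drug level only. The formal ANCOVA test is at Week 12, so the Week 4 and Week 8 misassignment does not enter it; what it affects is the reading of the two lower doses. It is worth correcting because the correction is cheap and, in a small trial, single records carry visible weight.

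**What to change.** Add a condition to SAP 9.4 and repeat it for DHEAS retests in SAP 10.3.1, since an edit to Table 4 alone would leave the retest route open.

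- **Week 4 and Week 8:** a fallback or retest DHEAS sample counts only if it precedes the first dose of the next level. SAP 9.3.14.3 already derives that date from dispensing. A morning sample on the dispensing date qualifies, because dosing is in the evening. Apply the rule to both arms by dispensing date, so that it can be programmed blind and does not create unequal missingness by design.
- **Week 12:** limit fallback and retest samples to last dose + 1 day, but only for subjects who completed dosing. Keep Week 12 samples from subjects who stopped early, as the estimand requires. A blanket cap would discard them. State that a sample on last dose + 1 belongs to Week 12, because Table 4 opens the Follow-up window on that day.
- **Reporting:** list every excluded sample with its study day and actual dose.

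The cost is a short SAP edit before database lock and no new data. A few values become missing for the visit analysis. They leave that visit's ANCOVA, and in the responder endpoints they count as non-response, which should be stated beside those results.

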10 STATISTICAL AND ANALYSIS ISSUES

10.1 Adjustments for Covariates

The categorical variables treatment group (0 = placebo, 1 = tildacerfont) will be used in statistical models for all efficacy analyses. The baseline value of continuous efficacy endpoints will be included in statistical models as a continuous covariate. Age will only be included as a continuous covariate in DHEAS analyses because DHEAS levels are known to decline with age. In general, the categorical, randomization stratification variable (i.e., Screening DHEAS value [0 = DHEAS \leq 1.2 \times ULN; 1 = DHEAS > 1.2 \times ULN]) will be used in efficacy analyses, except for analyses where the dependent variable is derived from DHEAS. For the analysis of change from baseline in DHEAS, the model will include the baseline serum DHEAS, as a continuous covariate in place of the randomization stratification variable.

10.2 Evaluating Normality

A probability plot (Quartile-Quartile [QQ] plot) of the residuals of each analysis model will be evaluated. A linear QQ plot indicates that the residuals follow a normal distribution, while any pattern in the QQ plot indicates deviations from normality. Homoscedasticity will be assessed with a scatter plot of residuals by predicted values. A uniform scatter pattern is indicative of homoscedasticity, while any pattern indicates heteroscedasticity.

10.3 Handling Dropouts or Missing Data

Every effort will be made by the Sponsor to ensure completeness of data collection. Missing data will not be imputed unless otherwise specified.

10.3.1 Handling of Laboratory Data

A retest value will be used if the first test is invalidated, e.g., specimen hemolyzed. For non-PK laboratory values that are continuous in nature but are presented as either above or below the respective quantitation limits (X), the following imputations will be made for the purposes of summarization:

- If value is listed as $< X$, then the imputed value will be $X/2$
- If a value is listed as $\leq X$, then the imputed value will be X
- If value is listed as $> X$, then the imputed value will be $X+1$
- If a value is listed as $\geq X$, then the imputed value will be X

10.3.2 Handling of Safety Data

10.3.2.1 Adverse Events

If the time of onset (before or after intake of study drug) cannot be determined whether an AE is treatment-emergent because of a partial onset date, the event will be counted as a TEAE.

Adverse events with incomplete start dates will be considered TEAEs, if:

- Day and month are missing and the year is equal to or after the year of the first date of study drug dosing;
- Month is missing and the year is after the year of the first date of study drug dosing;
- Day is missing and the year is equal to the year of the first date of study drug dosing and the month is equal to or after the month of the first date of study drug dosing; or
- Year is missing.

If severity or relationship of an AE to study drug is not recorded, the severity or relationship will be imputed as “severe” or relationship as “possibly related,” for analysis purposes. All efforts will be made to ensure no missing severity or relationship of an AE to study drug prior to database lock finalization.

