7.2.4. Time Period and Frequency for Event Assessment and Follow-up

AEs will be recorded from the time the ICF is signed until the end of the follow-up period. AEs will be assessed at each study visit, and subjects should be encouraged to contact the study site to report AEs that occur between scheduled visits. AEs that occur in the time period between

informed consent and the first dose of study drug of the Treatment Period should be recorded but will not be considered TEAEs.

After the initial AE/SAE report, the Investigator is required to proactively follow each subject at subsequent visits/contacts. All AEs/SAEs will be followed until resolution, stabilization, the event has been shown to be unrelated to study drug, or the subject is lost to follow-up (as defined in [Section 6.3](#)).

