10.3.2.2 Concomitant Medications

If the start date of a medication is missing, the medication will be considered to have started prior to the study. Such a medication may also be considered concomitant, depending on the stop date or lack thereof. If the stop date of a concomitant medication is missing, then the medication will be treated as ongoing. If the start date of a medication is missing, the stop date will be used to determine whether or not it is concomitant. Medications with other incomplete start dates or end dates will be imputed as follows:

Incomplete medication start date/time:

- If only have a YEAR, impute as Jan. 1.
- Else if only have YEAR and MONTH, impute as Day 1 of month.
- Otherwise missing, no imputation.

Incomplete medication end date/time:

- If only have a YEAR, impute as December 31.
- Else if only have YEAR and MONTH, then impute to last day of the month.
- Otherwise missing, no imputation.

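### An adverse event known to have ended before the first dose is still counted as treatment-emergent when its partial start date meets one of three listed conditions, because the SAP rule never looks at the stop date

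*SAP*

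**What the plan says.** SAP 10.3.2.1 opens with a general rule: where timing relative to the first dose cannot be settled "because of a partial onset date, the event will be counted as a TEAE". A specific rule follows, introduced by "Adverse events with incomplete start dates will be considered TEAEs, if", with four alternative conditions:

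1. "Day and month are missing and the year is equal to or after the year of the first date of study drug dosing"
2. "Month is missing and the year is after the year of the first date of study drug dosing"
3. the day is missing, the year is the dosing year, and "the month is equal to or after the month of the first date of study drug dosing"
4. "Year is missing"

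All four test the start date only. No other part of the SAP adds a stop-date check for adverse events.

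Other provisions bear on the point:

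- SAP 9.3.16 reserves the term TEAE for events that begin, or get worse, once dosing has started.
- Protocol 7.2.4 says that events falling between "informed consent and the first dose of study drug of the Treatment Period should be recorded but will not be considered TEAEs".
- Protocol 7.2.3 requires both start and end dates of every event in the eCRF.
- SAP 5.2.3.1 collects events from the first consent.
- SAP 10.3.2.2 says of medications: "If the start date of a medication is missing, the stop date will be used to determine whether or not it is concomitant".
- SAP section 4 gives the SAP precedence over the protocol where they differ on planned analyses.

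**The concern.** Counting an event as treatment-emergent when its timing is uncertain is a normal conservative convention. Here the rule also catches events whose timing is not uncertain. An event that stopped before the first dose neither began nor worsened on treatment, whatever is missing from its start date. The rule nevertheless places it in the TEAE tables, against the SAP's own definition.

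The protocol text does not clearly rescue the rule, because the SAP governs where the two conflict. SAP 9.3.17.1 also assigns each TEAE to the dose taken on its onset date, and a pre-dose event has no such dose.

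What is at stake is the accuracy of TEAE counts in small arms. False TEAEs can fall in either arm. In the placebo arm they would narrow a safety contrast rather than widen it.

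**Working it through.** The documents state no figure on this point, so there is none to reproduce. The check applies the four conditions to events that are over before dosing.

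**Step 1. Worked example.** First dose 20 June 2022; event stopped 15 June 2022. Under SAP 9.3.16 it is not a TEAE.

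| Recorded start | Condition met | Result under 10.3.2.1 |
|---|---|---|
| June 2022, day missing | third | TEAE (wrong) |
| 2022, day and month missing | first | TEAE (wrong) |
| Year missing | fourth | TEAE (wrong) |
| May 2022, day missing | none | not a TEAE (right) |
| 2021, day and month missing | none | not a TEAE (right) |

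The second condition needs a start year after the dosing year, so it cannot catch an event that ended before dosing. Three of the four conditions can misclassify.

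**Step 2. How often a condition is met, given a partial date.** Assumptions, for illustration only: the first dose is uniform over a 365-day year; the event starts uniformly over the W days before it; every event has resolved before the first dose. W = 30 is the screening limit (Protocol 3.1.2). W = 60 is the limit for the optional DHEAS visit (Protocol 3.1.2.1 and 12.1).

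- *Day missing.* With the first dose on day j of a month, the start is in the same month for j − 1 of the W possible start days. Summing j − 1 over a month gives 465 (31 days), 435 (30 days) or 378 (28 days). Over the year: 7 × 465 + 4 × 435 + 378 = 5,373. Share caught: 5,373/(365 × 30) = 49% for W = 30; 5,373/(365 × 60) = 25% for W = 60.
- *Day and month missing.* The event escapes only if it began in the previous calendar year, with probability (W + 1)/(2 × 365): 31/730 = 4% or 61/730 = 8%. Share caught: 96% or 92%.
- *Year missing.* Share caught: 100%.

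These are shares of events that already have the given partial date and ended before dosing. They are not shares of all adverse events. With a stop-date clause, every one becomes 0%.

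**Step 3. Effect of one subject.** SAP 14.1 counts subjects, not events, so one misclassified event moves a table row only if that subject would not otherwise be in it. The shift is then 1/n. With the planned arms (Protocol 8.1, SAP section 7):

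- placebo: 1/13 = 7.7 percentage points
- tildacerfont: 1/26 = 3.8 percentage points

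SAP section 15 reports that the study was discontinued early and ended with a small sample. The final arm sizes are not given; in smaller arms 1/n is larger.

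**The case against.** The best defence is that the opening sentence of 10.3.2.1 covers only events whose timing cannot be determined. A complete pre-dose stop date does determine it, so the conditions would merely resolve doubtful cases. This is a fair reading of the intent, but the text does not carry it. The opening sentence ties the doubt to the partial onset date, and the list then says that events meeting a condition are TEAEs, with no exception. A programmer following the list would count them.

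Second, the rule is conservative, applies alike in both arms, and is visible, since SAP 14.1 lists all adverse events. That stands, and it keeps the point minor. It does not make the classification right.

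Third, the medication rule is a weak comparator. SAP 9.3.15 defines concomitant use by overlap with treatment, so stop dates are needed there, whereas a TEAE is defined by onset or worsening. This also stands. Section 10.3.2.2 shows only that a stop-date check is familiar to the SAP, not that the adverse event rule breaks a general approach.

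A reader might infer more than the documents support:

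- *That any gap in the start date is enough.* It is not. A known month or year that already lies before the first dose meets no condition.
- *That dose-limiting toxicity counts would be inflated.* This needs Grade 3 or higher and at least possible relatedness (Protocol 6.1.1, SAP 9.3.16). An investigator would hardly relate an event that ended before any drug was taken. The remaining route is a missing relationship imputed as possible under 10.3.2.1, on top of a partial start date. That is too remote to rely on.
- *That the length of the pre-dose window measures the problem.* Calendar days are not an event rate. The optional visit schedules only consent and a DHEAS sample (Protocol 12.1), and the schedule's adverse event review row begins at Day 1 (SAP Table 7), although the text collects events from consent. The documents give no number of pre-dose events or partial dates.

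**Conclusion.** The point holds as a small error in a stated rule. Under SAP 10.3.2.1 an event with a recorded stop date before the first dose becomes a TEAE when its partial start date meets the first, third or fourth condition. That contradicts SAP 9.3.16 and Protocol 7.2.4.

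The direction is known: the rule can only add TEAEs. The number of events affected is unknown and may be zero, because each must both have such a partial date and have resolved before dosing. The per-subject shifts in the working rest on planned arm sizes and on the subject not already being counted in that row. The shares caught rest on the uniform-date assumptions and serve only to show that the conditions are easily met once a date is partial. Efficacy results are unaffected. Correcting the rule is worthwhile but not critical.

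**What to change.** Add to SAP 10.3.2.1, ahead of the list:

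> An AE whose stop date (or, if partial, its latest possible stop date) is before the first dose of study drug is not a TEAE, whatever part of its start date is missing. The rules below apply only to the remaining events, including those with a missing stop date.

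The latest possible stop date can follow the convention already used for medication end dates in SAP 10.3.2.2: last day of the month, or 31 December. Events with a missing stop date, or one on or after the first dose, keep the present conservative treatment. The cost is this short addition to the SAP and one condition in the program. No new data are needed, because end dates are already in the eCRF.
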